### **3.3    Study Subjects**

#### **3.3.1    Subject Disposition and Completion Status**

Subject disposition and completion status will be summarized for all subjects screened, and percentages will be based on subjects randomized and treated. In addition, disposition of subjects throughout the study with respect to discontinuation of treatment and end of study status including reasons will be provided. Summaries of the number and percentage of subjects entered at each site will be provided.

The mortality summary will include subjects with end of study status of death, as well as cause of death (toxicity related to IP or disease under investigation, or other).

Duration of follow-up will also be summarized.

A listing of global/country study disruptions (impacting visits, concomitant medications and/or exposure) will be provided.

#### **3.3.2    Demographics and Baseline Characteristics**

Demographics and baseline disease characteristics will be summarized for the ITT population. Demographic information related to sex, age, race, weight, height, and body mass index (BMI) will be presented by treatment group and for all subjects combined. A summary of smoking history will also be included. Tumor history including histology, stage, and pertinent biomarker results at the time of initial diagnosis and at study entry will be summarized. Baseline tumor characteristics including sum of target lesions diameters and ECOG performance status will also be summarized.

The summary for prior anticancer treatment will include the number and percent of subjects by treatment category (systemic therapy, radiation, cancer related surgery, other), number of prior systemic regimens and best response (complete response, partial response, stable disease, progressive disease, not evaluable, not applicable, per RECIST v1.1) to the most recent line of therapy, type of platinum agent (cisplatin, carboplatin, cisplatin and carboplatin, derived using the WHO Drug dictionary coded terms), time from last radiation to study drug initiation/randomization, and total amount of radiation received.

### **3.3.3 Study Drug Exposure**

- Treatment exposure will be summarized for the As-treated population. Duration of exposure to IP(s) in weeks and cycles will be summarized by descriptive statistics and by frequency. The duration of exposure for each IP is defined as below. last dose date plus the dosing interval (days) minus first dose date for subjects who completed treatment.
- minimum of (date of death plus 1 day, last dose date plus the dosing interval) minus first dose date for subjects who discontinued treatment.

Dose intensity and relative dose intensity of IP(s) will be summarized by descriptive statistics. The relative dose intensity is a percent of total actual dose that a subject received during corresponding study treatment period versus the total intended dose for the same study treatment period according to the study protocol. The details of the dose intensity calculation will be provided in the SPP as part of the standard exposure TFL templates.

Dosing deviations for IP(s), per the CRF, will be summarized with reasons for deviations for the following categories: delays, omissions, and interruptions. Duration of dosing delays will be derived where a delay is flagged on the CRF, based on the scheduled dosing dates and the visit window. The number of subjects with dosing delays and total dose delays will be summarized.

The use of subsequent anticancer treatment after the discontinuation of study treatment will be summarized by the type of subsequent anticancer treatment if data allow.

### **3.3.4 Concomitant Medications**

The number and percentage of subjects who took concomitant medications will be summarized by the ATC classification and the generic name coded by WHO Drug Dictionary Global B3 version March 2022 for the ITT Population. Concomitant medications will include all concomitant medications taken on or after the date of first dose of any IP or

any concomitant medication started prior to the first dose of study treatment that continued beyond the date of first dose of any IP.

### **3.3.5 Protocol Deviations**

The incidence of important protocol deviations will be summarized by deviation categories. The COVID-19 related IPDs will also be summarized. A listing will be provided with protocol deviation details. None of the deviations will lead to subjects being excluded from any analysis populations described in Section 3.2, unless otherwise specified. If a deviation is serious enough to have a potential impact on the primary analysis, sensitivity analyses may be performed.

## **3.4 Efficacy Analyses**

### **3.4.1 Primary Efficacy Endpoint(s) and Analyses**

#### **3.4.1.1 Primary Efficacy Endpoint(s) and Analysis**

The primary efficacy endpoint is objective response (OR) per Response Evaluation Criteria in Solid Tumors version 1.1 (RECIST v1.1). ORR is defined as the proportion of subjects with a best overall response of confirmed CR or confirmed PR that occur prior to disease progression, and/or prior to the initiation of subsequent anticancer treatment. Confirmation of response requirements are defined in [Section 3.4.2.1](#) for best overall response. The primary analysis of ORR will be based on the ITT population. An estimate of the difference in ORR as well as its 2-sided 95% exact CI between each experimental arm and control arm will be reported. The rates between each experimental arm and control arm will be tested for significance with a Cochran–Mantel–Haenszel test, stratified by histology (adenocarcinoma or non-adenocarcinoma). Subjects that have missing overall response assessments will be considered as non-responders, and will therefore be counted in the denominator, but not in the numerator of ORR. Primary efficacy analysis will include control subjects that are concurrently enrolled with each experimental arm.

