### **4.6 Treatment Assignment and Blinding**

#### **4.6.1 Methods for Assigning Treatment Groups**

Once confirmed that the subject meets eligibility criteria, an IXRS will randomize the subject to a treatment arm according to the randomization scheme.

A randomization method with dynamically changing randomization ratios will be employed to account for fluctuation in the number of treatment arms open for enrollment over the course of the study. Randomization will be stratified by histology (adenocarcinoma vs non-adenocarcinoma). The randomization scheme will use an equal ratio to all study treatment arms open for enrollment (eg, if experimental arms are opened sequentially, an experimental arm is added/closed, or enrollment in an experimental arm is suspended). Additionally, the following considerations regarding randomization will apply:

- If there is no experimental arm open for enrollment, then enrollment will be paused. Any subject who had consented previously and was in screening when the experimental arm(s) was closed due to safety concerns may be allowed to enter into the study but must be allocated to the control arm.
- Once the control arm enrolls 60 subjects, a subsequent randomization scheme may be initiated to optimize the number of subjects allocated to control arm.
- At any point during the study, the control arm will have no less than a 33% chance to be randomized in comparison to the active experimental arm that has the lowest randomization ratio in the study.

Study treatment must be administered within 3 days after the treatment arm is assigned. If there is a delay in the administration of study treatment such that it will not be administered within the specified timeframe, the study monitor must be notified immediately.

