Substantial changes to the protocol are summarized below.

- 1 Protocol synopsis; Section 3.1.1 (Overview), including Figure 1 (Study Flow Diagram); and Section 4.1.2 (Inclusion Criteria), Criterion 5: The window from the subject's last cCRT to randomization was increased from 28 days to 42 days to align with the PACIFIC study design and to provide sites more flexibility in identifying and enrolling subjects.
- 2 Section 4.1.3 (Exclusion Criteria): Added criterion (new Criterion 5) excluding subjects with prior exposure to any anti-PD-1, anti-PD-L1, or anti-CTLA-4 antibody for the treatment of NSCLC to avoid confounding factors affecting safety and efficacy assessments for this study.

Non-substantial changes to the protocol are summarized below.

- 1 Table 5 (Schedule of Screening and Treatment Period Procedures):
  - (a) Added assessment for ECOG performance status for Cycle 5 through Cycle 13. This assessment was inadvertently omitted in the original protocol. ECOG performance status is to be assessed throughout the study, as noted in Table 6 (Schedule of Follow-up Procedures) throughout the follow-up period and Table 7 (Schedule of Procedures for End of Study Visit).
  - (b) Footnote "e" revised to align with changes to required TSH tests described in Section 4.3.3, Other Safety Tests.
- 2 Table 6 (Schedule of Follow-up Procedures: Subjects Who Completed Study Treatment and Maintain DC, Subjects Who Discontinued Study Treatment Due to Other Reason Not Related to PD, and Subjects Who Experienced Unconfirmed PD and are Eligible for a Confirmation Scan):
  - (a) Clarified that disease assessments conducted as part of follow-up procedures  $\leq$  12 months from Cycle 1 Day 1 can be conducted within 7 days of the visit, in alignment with window for this assessment during the treatment period.
  - (b) Footnote "a" revised to align with changes to required TSH tests described in Section 4.3.3, Other Safety Tests.
- 3 Section 4.3.3 (Clinical Laboratory Tests), Other Safety Tests: Thyroid function tests were revised permitting sites to only conduct T3 or T4 tests when TSH is abnormal for flexibility to accommodate country or institutional guidelines regarding thyroidal abnormality screening. Additionally, it was clarified that free T3/free T4 are preferred over total T3/total T4 tests.
- 4 Section 4.5.1.8 (Reporting Product Complaints): Updated the telephone information in alignment with current contact.

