## 2.3 Treatment Assignment and Blinding

### Treatment Assignment

An interactive voice/web response system (IxRS) will be used to assign investigational product (IP) kit numbers to each subject who meets the eligibility criteria. A randomization method with dynamically changing randomization ratios will be employed to account for fluctuation in the number of treatment arms open for enrollment over the course of the study. The randomization will be stratified by histology (adenocarcinoma vs non-adenocarcinoma) and will use an equal ratio to all study treatment arms open for enrollment (e.g., if experimental arms are opened sequentially, an experimental arm is added/closed, or enrollment in an experimental arm is suspended). Additionally, the following considerations regarding randomization will apply:

- If there is no experimental arm open for enrollment, then enrollment will be paused. Any subject who had consented previously and was in screening when the experimental arm(s) was closed due to safety concerns may be allowed to enter into the study but must be allocated to the control arm.

- Once the control arm enrolls 60 subjects, a subsequent randomization scheme may be initiated to optimize the number of subjects allocated to control arm.
- At any point during the study, the control arm will have no less than a 33% chance to be randomized in comparison to the active experimental arm that has the lowest randomization ratio in the study.

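### The primary ORR comparison has no allocation-period stratum, so ORR drift can bias it if control allocation is lowered while an experimental arm is still enrolling

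*SAP*

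**What the plan says.** **Analysis.** SAP 3.4.1.1: "The rates between each experimental arm and control arm will be tested for significance with a Cochran–Mantel–Haenszel test", and that test is "stratified by histology (adenocarcinoma or non-adenocarcinoma"). On the control group: "Primary efficacy analysis will include control subjects that are concurrently enrolled with each experimental arm". The ORR difference is reported with an exact 95% interval and no stated stratification. The log-rank and Cox analyses of PFS and OS (SAP 3.4.2.4 and 3.4.2.5) are stratified by histology only. Protocol 4.8.3.1 names a chi-square or Fisher test without strata.

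**Allocation.** SAP 2.3: "A randomization method with dynamically changing randomization ratios will be employed"; the default scheme "will use an equal ratio to all study treatment arms open for enrollment". Once control has 60 subjects a different scheme may be started, subject to a floor: "the control arm will have no less than a 33% chance to be randomized in comparison to the active experimental arm" with the lowest ratio (Protocol 4.6.1; SAP 2.3 has the same rule). The synopsis lets arms open one after another or together, and SAP 2.4 expects more than 60 controls.

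**Sensitivity.** SAP 3.4.1.2 offers an optional comparison with all controls.

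**The concern.** Limiting the comparison to concurrent controls makes sense only if ORR may change over calendar time. That restriction removes drift from outside an arm's enrolment window. It removes drift inside the window only while the experimental-to-control ratio stays constant. If control allocation is cut partway through, the experimental arm has a larger share of its subjects in the later period than its controls have. A histology-only analysis then reads part of any calendar trend as a treatment effect.

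The primary comparison is affected, and so are the unstratified ORR difference and its interval. Upward drift favours the combination; downward drift hides a benefit. The optional all-controls analysis does not help, because it adds non-concurrent controls and has no period term.

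**Working it through.** **1. The plan's own figure.** For 30/60 against 18/60, an exact unconditional interval for the risk difference (Santner-Snell) gives 1.3% to 37.7%. This matches the stated 20% (1%, 38%) in SAP Table 2.4-1, and the other three rows also match after rounding. The half-width is (37.7 − 1.3)/2 = 18.2 points. The table assumes 60 per arm and no drift.

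**2. Allowed ratios.** If control's chance is 33% of the experimental arm's, the limit is about 1:3 control to experimental. If 33% is control's share of the pair, the limit is about 1:2. Under the default equal ratio, each experimental arm stays at 1:1 with control however many arms are open.

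**3. Bias.** Assume an arm of 60 opens after *m* controls, enrols 1:1 until control reaches 60, and then enrols *R* experimental subjects per control. The arm has 60 − m subjects before the change and m after. Its concurrent controls number 60 − m before and m/R after.

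Bias = drift × [m/60 − (m/R)/(60 − m + m/R)]

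| m | R | Experimental share, later period | Control share, later period | Gap | Bias, 10-point drift |
|---|---|---|---|---|---|
| 20 | 3 | 20/60 = 0.33 | 6.7/46.7 = 0.14 | 0.19 | 1.9 |
| 30 | 3 | 30/60 = 0.50 | 10/40 = 0.25 | 0.25 | 2.5 |
| 40 | 3 | 40/60 = 0.67 | 13.3/33.3 = 0.40 | 0.27 | 2.7 |
| 20 | 2 | 0.33 | 10/50 = 0.20 | 0.13 | 1.3 |
| 30 | 2 | 0.50 | 15/45 = 0.33 | 0.17 | 1.7 |
| 40 | 2 | 0.67 | 20/40 = 0.50 | 0.17 | 1.7 |

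Bias is in percentage points and is proportional to drift. The largest possible gap is 0.268 at R = 3 and 0.172 at R = 2.

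**4. Effect on the test.** These results come from 200,000 simulated trials per scenario. Assumptions: 30% base ORR, histology split 50/50 with equal ORR in both strata, one ratio change, and a nominal two-sided 5% level (the SAP sets none).

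- Constant 1:1 with a 20-point drift: no bias, type I error 4.6%.
- R = 3, 60 vs 40, histology only: a drift of +10 gives 5.6% two-sided, with 4.2% in the false-superiority tail (nominal 2.5%). A drift of +20 gives 7.5% and 6.9%.
- R = 2, 60 vs 42, histology only: a drift of +10 gives 5.2% and 3.5%.
- R = 3, true 20-point effect: power is 52% with no drift, 43% with a drift of −10 and 34% with −20.
- Histology by period: bias 0.0 to 0.1 points and type I error 4.9% to 5.1% in every null scenario.

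**5. Cost in precision** (m = 30, R = 3, 50% vs 30%).

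- Pooled: SE = √(0.25/60 + 0.21/40) = 9.7 points.
- By period, the Mantel-Haenszel weights are 30·30/60 = 15 and 30·10/40 = 7.5, or 2/3 and 1/3. The variances are 0.46/30 = 0.0153 and 0.25/30 + 0.21/10 = 0.0293.
- Stratified: SE = √(4/9 × 0.0153 + 1/9 × 0.0293) = 10.0 points, a rise of 3.4%.
- The same formula gives 2.6% at m = 20 and 3.7% at m = 40.
- With no drift and a true 20-point effect, power falls from 53.0% to 51.7% (R = 2, 60 vs 42) and from 51.7% to 49.0% (R = 3, 60 vs 40).

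**The case against.** The strongest reply is that the problem is doubly conditional. The post-60 scheme is optional, the 33% is a floor rather than a planned ratio, and ORR must also drift. The documents show neither event, so a reader who infers that the trial's primary comparison is in fact biased goes beyond them. This stands, and the point is worded accordingly.

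Four other inferences should be resisted.

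- **Changing ratios alone create the problem.** They do not. The general wording in SAP 2.3 ("A randomization method with dynamically changing randomization ratios will be employed to account for fluctuation in the number of treatment arms open for enrollment") comes with equal allocation, which keeps every experimental-to-control pair at 1:1 as arms open and close. Only the post-60 clause departs from that.
- **The amendments demonstrate drift.** Protocol section 9 says nobody was in Arm B before Amendment 2, so the irradiated-lesion criterion added then predates Arm B's enrolment, and the concurrent rule drops earlier controls. An arm opened with control at 1:1 reaches about 60 when control does and is barely exposed. What remains is the Amendment 3 change to the chemoradiotherapy window, which "was increased from 28 days to 42 days to align with the PACIFIC study design". Nothing ties it to a ratio change or to a shift in ORR.
- **A late arm's subjects fall mostly after the change.** In the table this is true only at m = 40. The bias needs only unequal shares.
- **The bias should be judged against the 8-point lower reference value.** That value belongs to the Bayesian Go rule in SAP 7.2, which does not use the CMH test and which this fix does not alter.

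It is also fair that the bias is small beside an 18-point half-width, and that the sample size was not set on power or Type I error (SAP 2.4). That limits the weight of the point. It does not remove it: the bias is systematic, it falls on the primary comparison, and wording can prevent it.

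**Conclusion.** The point holds as a conditional gap. As written, the plan allows the experimental-to-control ratio to change within an arm's enrolment window, and nothing in the analysis removes the resulting period effect. A 10-point drift would give about 1.9 to 2.7 points of bias at 1:3 and 1.3 to 1.7 at 1:2, in either direction. Two-sided type I error moves little at that drift (5.6% and 5.2% in the simulated cases), although the one-sided error is less balanced.

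These sizes rest on assumed values: the arm opens after 20 to 40 controls, there is a single ratio change when control reaches 60, and ORR drifts by 10 points. None of these is in the documents. No bias was computed for PFS or OS. An arm whose ratio stayed constant is not affected. This is an inexpensive improvement that should be made; it is not a fault that invalidates the design.

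**What to change.** Add to SAP 3.4.1.1:

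- For each experimental arm, state from the randomization record whether its ratio to control changed during its enrolment. If it did not, say so and leave the analysis as it is.
- If it did, define a new allocation period at each ratio change and stratify the CMH test by histology and allocation period. Report a period-stratified Mantel-Haenszel ORR difference with a matching stratified confidence interval, naming the interval method, alongside the exact unstratified interval.
- Add the same period stratum to the log-rank and Cox analyses in SAP 3.4.2.4 and 3.4.2.5.

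The periods should be set from the allocation record alone, without reference to outcomes.

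**Cost.** SAP wording and one further interval method. At 1:3 the standard error of the ORR difference rises by about 3 to 4% (9.7 to 10.0 points in the worked case), and power falls by roughly 1 to 3 points if there is no drift. Some cells will be thin: at m = 20 and 1:3, about 20/3 ≈ 7 later-period controls are split over two histology strata.

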#### **3.4.1.2 Additional Analyses of the Primary Efficacy Endpoint(s)**

The secondary analysis of ORR may be based on the Response-evaluable population, and/or Fisher's exact test. Sensitivity analyses may be provided based on a comparison between each experimental arm and all control subjects at the time of analysis.

### **3.4.2 Secondary Efficacy Endpoint(s) and Analyses**

The secondary efficacy endpoints include disease control (DC); duration of response (DoR); progression-free survival (PFS); progression-free survival at 12 months (PFS-12) and overall survival (OS). The efficacy endpoints will be summarized based on the ITT population and may be based on the Response-evaluable population as a supportive analysis. For analyses that involve an arm comparison between an experimental arm and control arm, only control subjects that are concurrently enrolled with the experimental arm will be included.

Efficacy analyses, except for OS, will be based on an application of Response Evaluation Criteria in Solid Tumors (RECIST) 1.1 ([Eisenhauer et al, 2009](#)) to investigator assessed tumor measurements.

Programmatic derivation guidance used for the application of RECIST v1.1 is provided in [Appendix 7.1](#). RECIST v1.1 guidelines will be used to determine disease response.

#### **3.4.2.1 Best Overall Response**

Best overall response (BOR) will be based on all post-baseline disease assessments that occur prior to disease progression, and/or prior to the initiation of subsequent anticancer treatment. BOR will be summarized with the number and percentage of subjects for the following categories: complete response (CR); partial response (PR); stable disease (SD); progressive disease (PD); and non-evaluable (NE). At least 7 weeks (8 weeks minus 1 week to allow for the protocol-defined disease assessment window) from randomization of IP must elapse without a subsequently radiological disease progression to assign a best overall response of SD.

Confirmation of CR and PR is required and must occur at least 4 weeks after initial documentation of CR or PR. If CR is pending confirmation and is designated at an assessment followed by 1 or more NE assessments, and/or PR assessments such that 1) the Target Lesion Response is CR and the Non-Target Lesion Response is NE, or 2) the Target Lesion Response is PR due solely to an increase in one or more lymph nodes to a size  $\geq 10$  mm and the Non-Target Lesion Response is either CR or NE, CR may be confirmed thereafter. Similarly, if a PR is pending confirmation and is designated at an assessment followed by 1 or more NE and/or SD assessments, PR may be confirmed thereafter.

In general, subjects not classifiable under the RECIST v1.1 response categories due to insufficient data or early death will be classified as NE for BOR but will be counted in the denominator of all response rate calculations. This generalization includes if a subject has missing lesion data at baseline. In this scenario, the subject will be classified as NE for BOR.

If a subject is missing lesion data at a disease assessment and yet PD criteria is met despite the missing data, the subject will be classified as PD.

